## 10.9 Other Procedures

The unblinded CGM procedure is described in the CGM section of the Manual of Operations (MOP).

## 11 ADVERSE EVENTS

### 11.1 Definitions

An **Adverse Event (AE)** (also referred to as an adverse experience) is any untoward medical occurrence (e.g., sign, symptom, disease, syndrome, intercurrent illness, clinically significant abnormal laboratory finding, injury, or accident) that emerges or worsens following administration of the study drug and until the end of study participation. The untoward medical occurrence may not necessarily have a causal relationship to the administration of the investigational product. An AE can therefore be any unfavorable and/or unintended sign (including a clinically significant abnormal laboratory result), symptom, or disease temporally associated with the use of a medicinal (investigational) product, whether or not related to the medicinal (investigational) product.

A **Suspected Adverse Reaction (SAR)** is any adverse event for which there is a reasonable possibility that the study drug caused the event. A reasonable possibility implies that there is evidence to suggest a causal relationship between the drug and the AE. Suspected adverse reaction implies a lesser degree of certainty about causality than adverse reaction.

An **Adverse Reaction (AR)** is any adverse event caused by the study drug.

**Serious Events, including SAE, Serious Suspected Adverse Reaction (SUSAR), or Serious Adverse Reaction (SAR)**, as determined by the PI or the Sponsor, are any event that results in any of the following outcomes:

- Death
- Life-threatening condition (i.e., the subject was, in the opinion of the PI, at immediate risk of death from the event as it occurred. It does not apply to an AE that hypothetically might have caused death if it were more severe)
- Persistent or significant disability/incapacity (i.e., the AE results in a substantial disruption of the subject's ability to carry out normal life functions)
- (Note: The term disability means a substantial disruption of a person's ability to conduct normal life functions. This definition is not intended to include experiences of relatively minor medical significance, such as uncomplicated headache, nausea, vomiting, diarrhea, influenza-like illness, or accidental trauma (e.g., sprained ankle),

which may interfere or prevent everyday life functions but do not constitute a substantial disruption.)

- In-patient hospitalization or prolongation of existing hospitalization (i.e., the AE required at least a 24-hour in-patient hospitalization or prolonged a hospitalization beyond the expected length of stay. Hospitalizations for elective medical/surgical procedures, scheduled treatments, or routine checkups are not SAEs by this criterion)
- Congenital anomaly/birth defect (i.e., an adverse outcome in a child or fetus of a subject exposed to the molecule or investigational product before conception or during pregnancy)
- Important medical event – does not meet any of the above serious criteria but may jeopardize the subject or may require medical or surgical intervention to prevent one of the outcomes listed above. Examples of such medical events include allergic bronchospasm requiring intensive treatment in an emergency room or at home, blood dyscrasias or convulsions that do not result in inpatient hospitalization, or the development of drug dependency or drug abuse

## **11.2 Pre-Existing Medical Conditions**

A pre-existing medical condition is one that is present prior to the start of the study and is to be reported as part of the subject's medical history. It should be reported as an AE only if the frequency, intensity, or the character of the condition worsens during the study.

## **11.3 Adverse Event Data Collection**

All adverse events that occur from the time of signing the informed consent document will be collected.

## **11.4 Treatment Emergent Adverse Event**

A treatment emergent adverse event (TEAE) is any AE reported after the initiation of study drug administration.

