#### 10.1.1 Screening Visit

Screening assessments and procedures may be performed in a single day or in multiple visits. Subjects should complete all screening procedures within 4 weeks of randomization even if some procedures need to be repeated. Note that subjects must be randomized within 5.0 years of T1D diagnosis, where diagnosis is defined as the first day of insulin use. All screening procedures including the MMTT could be completed in a single visit if the subject is using their own CGM and can share data with the site prior to the visit to allow site staff to ensure that the subjects meets criteria for adequate glycemic control (>55% of CGM readings within range of 70 – 180 mg/dL). In this case, subjects must be informed of the MMTT requirements in advance of the visit. Subjects must have CGM recording over 3 or more consecutive or non-consecutive days within 5 days prior to the screening MMTT to establish the adequacy of glycemic control. If preferred by the subject, or if additional time is required to complete all procedures (e.g. fundoscopic photography), additional screening visits may be scheduled as long as they fall within the screening period. If patients fail to meet the qualification criteria for HbA1c or other lab tests, the screening period may be extended an additional 4 weeks without repeating other screening tests. Randomization must occur within 4 weeks of the screening MMTT. The MMTT may be repeated to enable randomization if more than 4 weeks have elapsed since the initial screening MMTT. If a patient is using a closed-loop insulin pump it must be used in manual mode for the duration of the test.

Screening procedures include:

- Informed consent obtained or, for subjects aged 12-<18, assent and parental consent.
- Review of inclusion/exclusion criteria
- Review of medical history and diabetes history

- Physical examination
- Vital signs
- Height and weight
- Fundoscopic photography examination conducted by trained personnel and read by an ophthalmologist or optometrist who will provide a signed report.
- Collection of samples for laboratory assessments, including chemistry and hematology safety labs as described in Section 10.8 (including lipids, TSH, T1D antibody measurements, T-cell response, and HbA1c)
- Collection of sample for urinalysis, including protein screen
- If a urinary screen for protein is positive, a 24-hour urine collection for protein will be obtained

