## 11.8 Guidelines and Evaluation

### 11.8.1 Assessment and Recording

The PI is responsible for evaluating all AEs and determining the severity of the event. AEs will be collected from the time the subject signs informed consent until the time an event is resolved or until the subject completes or terminates from the study, whichever comes first.

The PI will assess subjects at each scheduled study visit post-treatment for the occurrence of AEs by observation of the subject and questioning the subject in an objective manner. In order to avoid bias in eliciting AEs, subjects should be asked the following non-leading question: *How have you felt since your last visit?* All AEs (serious and non-serious) reported by the subject must be recorded on the source documents and eCRFs. The PI should use the following definitions when assessing severity of an AE:

- Grade 1 = mild AE; subject is aware of symptoms or has minor findings. No interference with activity and no medical intervention/therapy required.
- Grade 2 = moderate AE; some interference with activity and/or minimal medical intervention/therapy required (clinical judgment should be used to determine what is a minimal intervention/therapy; short-term use of acetaminophen for a headache is an example of a minimal therapy).
- Grade 3 = severe AE; interferes significantly daily activity and/or requires more than minimal medical intervention/therapy.

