### **11.8.3 Reporting Requirements**

#### **11.8.3.1 Adverse Event Reporting**

Regardless of severity or relationship to the study product, all AEs occurring after informed consent and through the Month 36 study visit must be recorded in the subject's eCRF. The following information and assessments should be recorded in the AE section of the eCRF:

- The date of onset of the event and date it ended.
- The signs, symptoms, or diagnosis of the event.
- The AE severity using the criteria outlined above.
- The relationship of the event to the study drug.
- The seriousness of the event according to definitions outlined above.
- A description of any action taken regarding study drug disposition.
- Any additional data which might be relevant to the event.

All adverse events, regardless of the PI's determination as related or unrelated to the investigational product, are to be reported in the Advantage eClinical. AEs will be reviewed on a weekly basis by the medical monitor or his/her designee and cumulative AE reports will be shared with the data safety monitoring board per the charter. All SAEs will be reviewed within one business day of notification.

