	Screening	Screening MMTT	*Randomization	Week 1	Week 2	Week 3**	Week 4	Week 8	Week 12	Week 16	Week 20	Week 24	Week 28	Week 32	Week 36	Week 40	Week 44	Week 48	Week 52	Week 54
Concomitant medication use	X		X	X	X	X	X	X	X	X	X	X	X	X	X	X	X	X	X	X
Adverse events	X		X	X	X	X	X	X	X	X	X	X	X	X	X	X	X	X	X	X
Self-report of hypoglycemic events	X	X	X	X	X	X	X	X	X	X	X	X	X	X	X	X	X	X	X	
Self-report of administration of at-home injections							X	X	X	X	X	X	X	X	X	X	X	X	x	X

\*Randomization could be up to 8 weeks from Screening Visit to allow for any laboratory tests to be repeated

\*\* Visit for first 6 subjects in Cohort B only

aBrief Physical Exam

bHematology: CBC with differential and platelet count

cChemistry: Electrolytes (sodium, potassium, chloride, bicarbonate), BUN, creatinine, glucose, albumin, calcium, AST, alkaline phosphatase, total bilirubin, total protein, creatine kinase, total cholesterol, HDL cholesterol, LDL cholesterol, triglycerides

dSample for lipids should be collected in a fasted state. The screening sample will be collected at 10 minutes prior to Boost administration in the MMTT. Samples at weeks 12, 24, and 52 will be collected with other chemistry samples in 10 minutes prior to Boost administration in the MMTT. UPT results must be negative for dosing to continue

ePrior to study drug administration

fSerology: Hepatitis B, Hepatitis C, HIV

gT1D antibodies: GAD65, IA-2, insulin ZnT8

hContinuous glucose monitoring will be initiated 5 days or more before the screening MMTT visit and continued until the Week 52 visit.

iStudy drug administration shown for in-office visits.

j For subjects aged 12-<18 only

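### Section 11.4 defines a treatment-emergent AE by when it is reported, not when it starts or worsens, and Section 11.1 contradicts the sections that collect AEs from consent (minor)

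*Protocol*

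**What the plan says.** Section 11.4 defines a TEAE in one sentence: it "is any AE reported after the initiation of study drug administration". Onset and worsening are not mentioned.

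The protocol gives two starting points for an AE:

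- **After study drug.** Section 11.1 describes an AE as an untoward occurrence "that emerges or worsens following administration of the study drug and until the end of study participation".
- **From consent.** Section 11.3 states: "All adverse events that occur from the time of signing the informed consent document will be collected". Section 11.8.1 agrees: "AEs will be collected from the time the subject signs informed consent". Section 11.8.3.1 adds that "all AEs occurring after informed consent and through the Month 36 study visit must be recorded in the subject's eCRF". Section 11.8.3.2 starts SAE capture at consent too, and the adverse-event row in Appendix 1 begins at Screening.

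On the length of screening, Section 10.1.1 says: "Subjects should complete all screening procedures within 4 weeks of randomization". It allows a further 4 weeks if HbA1c or other laboratory criteria are not met. The Appendix 1 footnote gives the outer limit: "Randomization could be up to 8 weeks from Screening Visit".

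The AE form already holds the item needed to classify by onset. Section 11.8.3.1 lists: "The date of onset of the event and date it ended".

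**The concern.** A treatment-emergent category exists to separate events that could be due to the drug from those that could not. The relevant date is when the event began or got worse. The date on which the site heard of it depends on recall, visit timing and monitoring. A rule tied to that date can admit an event that preceded the first dose and can miss one that worsened after it.

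Section 11.1 does not settle the matter. If nothing before the first dose is an AE, the instructions to collect AEs and SAEs from consent have no object. TEAE also becomes almost the same as AE, although Section 11.4 defines it separately and Section 13.3.2 summarises it as a category of its own. Two programmers working from this text could build different TEAE flags and each cite the protocol.

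Safety over 52 weeks is the stated Primary Safety Objective. Section 13.3.2 calls for monthly TEAE incidence summaries on live data, with the groups labelled A and B, and an excessive rate of a specific AE or SAE may lead to DSMB referral. Events that cannot be due to the drug add noise to those summaries.

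**Working it through.** **1. Screening length.** Section 10.1.1 gives 4 weeks plus a permitted extension of 4 weeks: 4 + 4 = 8 weeks, which agrees with the Appendix 1 footnote. Eight weeks is a ceiling, reached only when laboratory tests must be repeated. Section 14 quotes up to 4 weeks.

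**2. Four kinds of event under the competing texts.**

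| Event | 11.4 with AE as in 11.1 | 11.4 with AE as in 11.3 and 11.8 | Onset-or-worsening rule |
|---|---|---|---|
| Starts in screening, first recorded after first dose, no worsening | Not an AE, so not a TEAE | TEAE | Not a TEAE |
| Starts and is reported in screening, worsens after first dose | AE by worsening; TEAE if the worsening is reported | Already reported before drug; may be left out unless entered again | TEAE |
| Starts and is reported in screening, no worsening | Not an AE, so not a TEAE | AE, not a TEAE | Not a TEAE |
| Starts and is reported after first dose | TEAE | TEAE | TEAE |

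The texts diverge in the first two rows. In both, the from-consent reading of Section 11.4 gives the wrong class or leaves it open.

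**3. How an event could reach the first row.** Section 11.8.3.3 has site staff look for unreported AEs and has monitors prompt sites to enter any they find. A screening event found in this way after dosing has a pre-dose onset and a post-dose report.

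**4. Size.** The protocol gives neither an AE rate nor a rate of late reporting, so the number of misclassified events cannot be computed. The direction can be shown under assumptions. Suppose the true TEAE incidence for a term is 30% v 20% (risk ratio 1.50). Suppose also that a fraction q of subjects in each arm, independently of true TEAEs, has a pre-dose event of that term recorded late. All these inputs are assumed. Then the observed incidence is 1 − (1 − p)(1 − q):

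- q = 1%: 1 − 0.70 × 0.99 = 30.7%; 1 − 0.80 × 0.99 = 20.8%; ratio 1.48
- q = 2%: 31.4% v 21.6%; ratio 1.45
- q = 5%: 33.5% v 24.0%; ratio 1.40
- q = 10%: 37.0% v 28.0%; ratio 1.32

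The ratio moves toward 1 throughout. At the low values of q it hardly moves.

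**The case against.** The strongest defence is that Section 11.4 speaks of an AE and Section 11.1 already requires an AE to arise or worsen after drug. Read together, a purely pre-dose event is never a TEAE. Section 11.2 points the same way by sending conditions present before the study to medical history unless they worsen. This reading is available, but it conflicts with Sections 11.3, 11.8.1, 11.8.3.1 and 11.8.3.2 and leaves the TEAE category nearly redundant. It shows that the text is contradictory, not that the rule is sound.

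The practical safeguards do stand. Section 10.1.2 lists AE review at the randomization visit ahead of dosing, so screening events mentioned by then are not TEAEs even on the literal wording. The scripted question in Section 11.8.1 asks about the time since the previous visit, so at Week 1 it covers the period from the first dose. Only late-recorded events are exposed.

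A reader might go further and infer three things that the protocol does not support:

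- **That up to 8 weeks of screening events would routinely enter the TEAE counts.** The pre-dose review and the usual 4-week screening argue against this.
- **That the planned significance test is compromised.** The Fisher's Exact test in Section 13.3.2 names the most frequent AEs or SAEs, not TEAEs. The TEAE summaries there are the monthly A/B tables.
- **That a risk ratio would fall from 1.50 to 1.32.** That needs the assumed 10% late-reporting rate, which has no basis in the protocol; 2% gives 1.45.

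The SAP is not shown and may define TEAEs by onset. If it does, it departs from what Section 11.4 states, and the protocol sentence still needs correcting.

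**Conclusion.** The point holds as a minor one. Section 11.4 fixes a TEAE rule on the wrong date, and Section 11.1 contradicts the from-consent sections in a way that leaves the rule unsettled. Misclassification can go in two directions: late-recorded screening events may be counted, and screening events that worsen on treatment may be missed.

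This consequence depends on reading AE in the from-consent sense of Sections 11.3 and 11.8. The number of events involved is unknown and probably small. The conclusion that a difference would be diluted, not biased in favour of one arm, assumes that reporting delays are alike in the two blinded arms. The collected data are not damaged, because the onset date allows the flag to be derived correctly.

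**What to change.** Reword Section 11.4 so that a TEAE is an AE whose onset, or whose worsening in frequency or intensity, falls on or after the first dose, determined from the recorded onset date. Amend Section 11.1 to agree with Sections 11.3 and 11.8, so that events between consent and first dose are AEs that are not treatment-emergent. State that worsening of an event already reported in screening is entered with its own date, so that it can be classified. Check that the SAP uses the same definition.

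The cost is one sentence in each of two sections and a line of form guidance. No new data item is needed, and clinical management and the planned tests are unchanged.

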## **11.5 Unexpected Event**

An AE is considered unexpected from a regulatory perspective when it is not listed in the package insert/prescribing information, Investigator's Brochure (IB), or, if none of these is available, the general investigational plan (e.g., study protocol, informed consent) for the study product at the specificity and severity that has been observed. Unexpected is a regulatory term, whereas unanticipated is more clinical and should not be used interchangeably. For example, some AEs can be anticipated to occur as a result of a disease or in an older population (e.g., cancer-related deaths in a cancer trial, strokes or acute myocardial infarctions in an older population). However, for reporting purposes, these

anticipated events are not “expected” because they are not listed in the IB (i.e., the study product is not suspected or known to cause them). The Sponsor or designee is responsible for determining expectedness.

## 11.6 Adverse Events of Special Interest

Local injection site reactions will be graded according to scale show below.

Local reactions (at the injection site)	Severity grade
Injection Site Pain, Burning, Itching or Tenderness	
Pain, burning, or tenderness, mild in intensity causing no limitation of use of limb	1 (Mild)
Pain, burning or tenderness moderate in intensity causing minimal impairment of mobility, mental concentration, or sleep	2 (Moderate)
Pain, burning, or tenderness causing significant impairment of mobility, mental concentration or sleep	3 (Severe)
Redness (Erythema)	
Longest diameter: 2.5 to < 5 cm	1 (Mild)
Longest diameter: ≥ 5 to < 10 cm	2 (Moderate)
Longest diameter: ≥ 10 cm OR Potentially life-threatening consequences (e.g., abscess, exfoliative dermatitis, necrosis involving dermis or deeper tissues)	3 (Severe)
Swelling (Induration)	
Longest diameter: 2.5 to < 5 cm	1 (Mild)
Longest diameter: ≥ 5 to < 10 cm	2 (Moderate)
Longest diameter: ≥ 10 cm OR Potentially life-threatening consequences (e.g., abscess, exfoliative dermatitis, necrosis involving dermis or deeper tissues)	3 (Severe)
Ulceration, Subcutaneous abscess	
Longest diameter: 2.5 to < 5 cm	1 (Mild)
Longest diameter: ≥ 5 to < 10 cm	2 (Moderate)
Longest diameter: ≥ 10 cm	3 (Severe)
Bruising	

Local reactions (at the injection site)	Severity grade
Longest diameter: 2.5 to < 5 cm	1 (Mild)
Longest diameter: ≥ 5 to < 10 cm	2 (Moderate)
Longest diameter: ≥ 10 cm	3 (Severe)
Systemic Reactions	1 (Mild); 2 (Moderate); 3 (Severe)
Allergic Reactions	1 (Mild); 2 (Moderate); 3 (Severe)

## 11.7 Vital Signs and Physical Exam Findings and Laboratory Results

Vital signs and physical exam and laboratory findings will be captured on specific eCRFs. Vital signs and physical exam or laboratory results assessed as clinically significant should be entered as an individual AE or documented as part of a broader diagnosis reported as an AE in the Advantage eClinical system.

Abnormal laboratory findings (e.g., clinical chemistry, hematology) or other abnormal assessments (e.g., vital signs) that are judged by the PI to be clinically significant will be recorded as AE and as SAE if they meet any seriousness criteria outlined previously.

Clinically significant abnormal laboratory findings or other abnormal assessments that are detected during the study or are present at screening and significantly worsen following the start of the study will be reported as AE. However, clinically significant abnormal laboratory findings or other abnormal assessments that are associated with the disease being studied, unless judged by the PI as more severe than anticipated for the subject's condition, or that are present or detected at the start of the study but do not subsequently worsen, will not be reported as AE. The PI will exercise medical judgment in deciding whether abnormal laboratory values or other abnormal assessments are clinically significant while also considering the normal range for age and gender, among other factors.

## 11.8 Guidelines and Evaluation

### 11.8.1 Assessment and Recording

The PI is responsible for evaluating all AEs and determining the severity of the event. AEs will be collected from the time the subject signs informed consent until the time an event is resolved or until the subject completes or terminates from the study, whichever comes first.

The PI will assess subjects at each scheduled study visit post-treatment for the occurrence of AEs by observation of the subject and questioning the subject in an objective manner. In order to avoid bias in eliciting AEs, subjects should be asked the following non-leading question: *How have you felt since your last visit?* All AEs (serious and non-serious) reported by the subject must be recorded on the source documents and eCRFs. The PI should use the following definitions when assessing severity of an AE:

- Grade 1 = mild AE; subject is aware of symptoms or has minor findings. No interference with activity and no medical intervention/therapy required.
- Grade 2 = moderate AE; some interference with activity and/or minimal medical intervention/therapy required (clinical judgment should be used to determine what is a minimal intervention/therapy; short-term use of acetaminophen for a headache is an example of a minimal therapy).
- Grade 3 = severe AE; interferes significantly daily activity and/or requires more than minimal medical intervention/therapy.

